8.1.3 CCI [Redacted]

CCI [Redacted]

8.1.4 PWCG3 PSA criteria

All patients should have PSA collected **CCI** at screening, at the start of each new treatment cycle, at the end of study treatment, and as indicated in the SoA of each module. PSA **CCI** should also be collected when clinically indicated as per Investigator discretion.

PWCG3 PSA criteria are located in [Appendix I](#).

8.2 Safety assessments

Planned time points for all safety assessments are provided in the module-specific SoA.

8.2.1 Clinical safety laboratory assessments

See [Table 8](#) for the list of clinical safety laboratory tests to be performed and the screening and module-specific SoA for the timing and frequency. All protocol-required laboratory assessments, as defined in the table, must be conducted in accordance with the laboratory manual and the SoAs.

The Investigator should make an assessment of the available results with regard to clinically relevant abnormalities. The laboratory results should be signed and dated and retained at the study center as source data for laboratory variables.

For information on how AEs based on laboratory tests should be recorded and reported, see [Section 8.3.7](#).

Additional safety samples may be collected if clinically indicated at the discretion of the Investigator. The date, time of collection and results (values, units and reference ranges) will be recorded on the appropriate eCRF.

Safety laboratory assessments will be performed locally at each study site laboratory by means of their established methods. Therefore, the number of samples/blood volumes is subject to site-specific change.

Laboratory values that meet the criteria for CTCAE Grade 3 or have changed significantly from baseline and are considered to be of clinical concern will be repeated/confirmed within 7 days and followed up as appropriate.

Table 8 Laboratory safety variables

Hematology	Clinical chemistry
Blood (B)-Hemoglobin	Albumin
B-Leukocyte	Alkaline phosphatase ^b
B-Absolute leukocyte differential count:	ALT ^b
• Neutrophils ^a	Amylase ^c
• Lymphocytes ^a	AST ^b
• Monocytes	Bicarbonate HCO ₃ ^d
• Basophils	Calcium, total
• Eosinophils	Chloride ^d
B-Platelet count	Creatinine ^{d, e}
	Gamma glutamyltransferase (GGT) ^d
Coagulation	Glucose
Prothrombin Time	Lactate dehydrogenase (LDH)
Or	Lipase ^c
International normalization ratio (INR) and activated partial thromboplastin time (aPTT)	Magnesium ^d
	Phosphate
Urinalysis	Potassium
Bilirubin, blood, color and appearance, glucose, ketones, pH, protein, and specific gravity	Sodium
	Total bilirubin ^b
Additional Tests	Total protein
Testosterone	Thyroid stimulating hormone ^f
Prostate specific antigen (PSA)	Free T4 ^g
Hepatitis A, hepatitis B surface antigen, hepatitis C antibody, and HIV antibody ^{h, i, j, k}	Free T3 ^g
CCI	Urea nitrogen
	Uric acid
	C-reactive protein (CRP)

^a Can be recorded as absolute counts or as percentages. Absolute counts will be calculated by Data Management if entered as percentage. Total white cell count therefore has to be provided.

^b Tests for ALT, AST, alkaline phosphatase, and total bilirubin must be conducted and assessed concurrently. If total bilirubin is $\geq 2 \times$ upper limit of normal (and no evidence of Gilbert's syndrome), then fractionate into direct and indirect bilirubin.

- c It is preferable that both amylase and lipase parameters are assessed. For sites where only 1 of these parameters is routinely measured, either lipase or amylase is acceptable.
- d Bicarbonate (where available), chloride, creatinine clearance, gamma glutamyltransferase, magnesium, testing are to be performed at baseline, on Day 1 (unless all screening laboratory clinical chemistry assessments are performed within 3 days prior to Day 1), and if clinically indicated.
- e Creatinine clearance will be calculated by data management using Cockcroft-Gault (using actual body weight).
- f If TSH is measured within 14 days prior to Day 1 (first infusion day), it does not need to be repeated at Day 1.
- g Free T3 or free T4 will only be measured if TSH is abnormal or if there is a clinical suspicion of an AE related to the endocrine system.
- h Hepatitis A testing will only be performed if the patient is considered symptomatic per the Investigator.
- i Hepatitis B testing: hepatitis B surface antigen, hepatitis B surface antibody, hepatitis B core antibody, IgM hepatitis B core antibody. If hepatitis B core (total) antibody testing is unavailable, then the hepatitis B core IgG and IgM should both be obtained instead. If a test is not locally available, then standard local practice for assessing hepatitis B status should be utilized. If screening tests are positive, a HBV-DNA test should be obtained to assess infection status.
- j Hepatitis C antibody. If screening antibody is positive, an HCV-RNA test should be performed to assess infection status.
- k Human immunodeficiency virus-1 antibody

Note: In case a patient shows an AST **or** ALT $\geq 3 \times \text{ULN}$ together with TBL $\geq 2 \times \text{ULN}$ please refer to [Appendix E](#) “Actions required in cases of increases in liver biochemistry and evaluation of Hy’s Law” for further instructions.

8.2.2 Physical examinations

A complete physical examination will be performed and include an assessment of the following: general appearance, respiratory, cardiovascular, abdomen, skin, head and neck (including ears, eyes, nose and throat), lymph nodes, thyroid, musculo-skeletal (including spine and extremities) and neurological systems.

Physical examination will be performed at visits as specified in the module-specific SoA. Investigators should pay special attention to clinical signs related to previous serious illnesses. New or worsening abnormalities may qualify as AEs (see Section 8.3.7 for details).

Significant abnormal findings will be recorded in the Medical History or as an AE. Abbreviated symptom-directed physical examinations will be conducted at subsequent visits post-dosing.

8.2.3 Performance status

Performance status will be assessed as indicated in the Study Plan figures according to ECOG criteria as follows:

0 = Fully active, able to carry out all pre-disease activities without restrictions

- 1 = Restricted in physically strenuous activity but ambulatory and able to carry out work of a light or sedentary nature e.g., light housework, office work
- 2 = Ambulatory and capable of self-care, but unable to carry out any work activities. Up and about more than 50% of waking hours
- 3 = Capable of only limited self-care, confined to bed or chair more than 50% of waking hours
- 4 = Completely disabled, cannot carry on self-care, totally confined to bed or chair.

8.2.4 Vital signs

Vital signs (pulse rate, systolic and diastolic BP, respiration rate, and temperature) will be assessed according to the screening and module-specific SoA. Body weight is also recorded at each visit and height is recorded at screening.

- Blood pressure and pulse measurements will be assessed with a completely automated device. Manual techniques will be used only if an automated device is not available.
- Blood pressure and pulse measurements should be preceded by at least 10 minutes of rest for the patient in a quiet setting without distractions (e.g., television, cell phones).
- For the baseline BP measurement, 2 or more readings should be taken at 2-minute intervals and averaged. If the first 2 diastolic readings differ by more than 5 mmHg, then an additional reading should be obtained. For all other subsequent measurements, institutional standards for measuring vital signs should be followed.

If antihypertensive management is initiated during the study, more frequent BP monitoring should be initiated until a stable antihypertensive regimen has been established.

Additional assessments may be performed at the discretion of the Investigator, if clinically indicated.

8.2.5 Electrocardiograms

Electrocardiograms (ECGs) will be obtained at screening, end of treatment, and when clinically indicated.

Resting 12-lead ECG

Twelve-lead ECGs will be obtained after the patient has been resting supine for at least 10 minutes prior at times indicated in the screening and module-specific SoA. All ECGs should be recorded with the patient in the same physical position.

For each time point 3 ECG recordings should be taken about a minute apart within a 5-minute window per timepoint. A standardized ECG machine should be used and the patient should be examined using the same machine throughout the study, when feasible.

The ECG traces will be recorded and reviewed as per the study-specific ECG manual. The Investigator or designated physician will review each of the ECGs and may refer the patient to a local cardiologist, if appropriate. If an abnormal ECG finding at screening or baseline is considered to be clinically significant by the Investigator, it should be reported as a concurrent condition. During the study, clinically significant abnormal ECG findings not present at baseline should be reported as an AE (if present, the clinical signs and symptoms associated with the abnormal finding should be reported as the AE with the ECG abnormality given as explanatory information). For all ECGs details of rhythm, PR, R-R, QRS and QT intervals and an overall evaluation will be recorded on the eCRF.

8.2.6 Echocardiography or multi-gated acquisition scan

An echocardiogram (ECHO) should be performed at screening (≤ 14 days prior to Cycle 1 Day 1) and within 14 days after a clinically significant ECG finding (T wave inversion/flattening). If an ECHO cannot be taken, a cardiac MRI or multigated acquisition (MUGA) scan to assess left ventricular ejection fraction will be conducted. In case of any T wave abnormality, the ECHO, MRI, or MUGA should be repeated at the end of treatment (EOT) visit to address the question of recovery during the off-treatment period.

8.2.7 End-of-treatment visit

Patients will return to the clinic for an EOT visit that is to be performed as soon after the study drug is stopped as possible, preferably within 2 days of stopping drug. For patients who have had drug held prior to the decision for discontinuation, the EOT visit should be performed within 7 days of the decision. Tumor assessments will be done at this visit, if they have not been performed within the past 2 months. Other assessments to be performed are presented in the SoA in the modular-specific appendix.

8.2.8 Follow-up visits

8.2.8.1 30-day follow-up visit

A safety follow-up visit will be performed approximately 30 (± 7) days after the study drug(s) is (are) permanently discontinued, unless the patient withdraws consent. The primary purpose of this visit is to follow up on any AEs ongoing at the time of study treatment discontinuation and to assess any new AEs that may have occurred since discontinuation. In addition, any new medications will be recorded. This information can be collected by phone. Any AE, SAE, or abnormal laboratory findings that are ongoing at the time of study treatment discontinuation, or any new events within 30 days of last study treatment unless otherwise indicated in the specific module, must be followed up to resolution or until the event becomes

stable (or returns to baseline) or is unlikely to resolve further in the opinion of the Investigator.

8.2.8.2 Progression-free follow-up visits

Patients who discontinue study treatment prior to the occurrence of objective PD will be followed with PSA samples and CT/MRI/PET and bone scans every 3 months (± 1 week) from the last date of the last tumor response assessment until either: objective PD has been confirmed, withdrawal of consent, until the primary analysis DCO, or until the study or module is terminated by the Sponsor.

8.2.8.3 Survival follow-up

Patients will be followed every 3 months after the last dose of study drug for survival until withdrawal of consent, or until the primary DCO for the study. The survival and subsequent cancer therapy follow-up can be done by a medical record review or telephone call at the Investigator's discretion.

When required, survival calls will be made in the week following the date of DCO for the analysis, and if participants are confirmed to be alive or if the death date is after the DCO date, these participants will be censored at the date of DCO. When required, the status of ongoing, withdrawn (from the study), and "lost to follow-up" participants at the time of the OS analysis should be obtained by the site personnel by checking the participant's notes, hospital records, contacting the participant's general practitioner and checking publicly-available death registries. In the event that the participant has actively withdrawn consent to the processing of their personal data, the vital status of the participant can be obtained by site personnel from publicly available resources where it is possible to do so under applicable local laws.

8.2.9 COVID-19 Testing

Tests for active COVID-19 infection may be prescribed, where appropriate, and in accordance with local procedures. If a patient tests positive, their continued participation in the study and treatment with the study drugs will be discussed with the Medical Monitor

8.3 Collection of adverse events

The Principal Investigator is responsible for ensuring that all staff involved in the study are familiar with the content of this section.

The definitions of AEs and SAEs can be found in [Appendix B](#).

AEs will be reported by the patient (or, when appropriate, by a caregiver, surrogate, or the patient's legally authorized representative).

The Investigator and any designees are responsible for detecting, documenting, and recording events that meet the definition of an AE or SAE. For information on how to follow up AEs see Section [8.3.3](#).

8.3.1 Method of detecting AEs and SAEs

Care will be taken not to introduce bias when detecting AEs and/or SAEs. Open-ended and non-leading verbal questioning of the patient is the preferred method to inquire about AE occurrences.

8.3.2 Time period and frequency for collecting AE and SAE information

Adverse events, including SAEs, will be collected from time of signature of ICF throughout the treatment period and including the 30-day follow-up period, unless specified differently in each module (see module-specific guidance).

All SAEs will be recorded and reported to the Sponsor or designee within 24 hours, as indicated in [Appendix B](#). The Investigator will submit any updated SAE data to the Sponsor within 24 hours of it being available.

Investigators are not obligated to actively seek AEs or SAEs in former study patients. However, if the Investigator learns of any SAE, including a death, at any time after a patient's last visit and he/she considers the event to be reasonably related to the study treatment or study participation, the Investigator may notify the Sponsor.

The methods of recording, evaluating, and assessing causality of AEs and SAEs and the procedures for completing and transmitting SAE reports are provided in [Appendix B](#).

8.3.3 Follow-up of AEs and SAEs

After the initial AE/SAE report, the Investigator is required to proactively follow each patient at subsequent visits/contacts. All SAEs/non-serious AEs/AEs of special interest (AESIs) (see module-specific guidance) will be followed until resolution, stabilization, the event is otherwise explained, or the patient is lost to follow-up

Any AEs that are unresolved at the patient's last AE assessment or visit in the study will be followed up by the Investigator for as long as medically indicated, but without further recording in the eCRF. AstraZeneca retains the right to request additional information for any patient with ongoing AEs/SAEs at the end of the study, if judged necessary.

8.3.4 Adverse event data collection

The following variables will be collected for each AE:

- AE (verbatim)

- The date when the AE started and stopped
- CTCAE grade/maximum CTCAE grade
- Whether the AE is serious or not
- Investigator causality rating against the IP(s) (yes or no)
- Action taken with regard to IP(s)
- Action taken with regard to procedure or concomitant medication
- Outcome
- Does the Investigator consider this AE an ImAE?

In addition, the following variables will be collected for SAEs:

- Date AE met criteria for serious AE
- Date Investigator became aware of serious AE
- AE is serious due to which criterion
- Date of hospitalization
- Date of discharge
- Probable cause of death
- Date of death
- Autopsy performed
- Causality assessment in relation to study procedure(s)
- Causality assessment in relation to other medication

8.3.5 Causality collection

The Investigator will assess causal relationship between IP and each AE, and answer “yes” or “no” to the question “Do you consider that there is a reasonable possibility that the event may have been related to the IP?”

For SAEs, causal relationship will also be assessed for other medication and study procedures. Note that for SAEs that could be associated with any study procedure the causal relationship is implied as “yes”.

A guide to the interpretation of the causality question is found in [Appendix B](#) to the Clinical Study Protocol.

8.3.6 Adverse events based on signs and symptoms

All AEs spontaneously reported by the patient or reported in response to the open question from the study site staff: “Have you had any health problems since the previous visit?”, or revealed by observation will be collected and recorded in the eCRF. When collecting AEs, the recording of diagnoses is preferred (when possible) to recording a list of signs and symptoms. However, if a diagnosis is known and there are other signs or symptoms that are

not generally part of the diagnosis, the diagnosis and each sign or symptom will be recorded separately.

8.3.7 Adverse events based on examinations and tests

The results from the protocol mandated laboratory tests and vital signs will be summarized in the clinical study report (CSR). Deterioration as compared to baseline in protocol-mandated laboratory values, vital signs, ECGs, or other safety assessments should therefore only be reported as AEs if they fulfil any of the SAE criteria or are the reason for discontinuation of treatment with the IP.

If deterioration in a laboratory value/vital sign is associated with clinical signs and symptoms, the sign or symptom will be reported as an AE and the associated laboratory result/vital sign will be considered as additional information. Wherever possible the reporting Investigator will use the clinical rather than the laboratory term (e.g., anemia versus low hemoglobin value). In the absence of clinical signs or symptoms, clinically relevant deteriorations in non-mandated parameters should be reported as AE(s).

Deterioration of a laboratory value which is unequivocally due to disease progression should not be reported as an AE/SAE.

Any new or aggravated clinically relevant abnormal medical finding at a physical examination as compared with the baseline assessment will be reported as an AE unless unequivocally related to the disease under study (see Sections 8.3.9 and 8.3.10).

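### Sections 8.2.5 and 8.3.7 give opposite instructions on whether a new, clinically significant but non-serious ECG finding is recorded as an AE

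*Protocol*

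**What the plan says.** Two current sections of the core protocol deal with ECG findings as adverse events.

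- **Section 8.2.5 (Electrocardiograms).** During the study, "clinically significant abnormal ECG findings not present at baseline should be reported as an AE". Where symptoms accompany the finding, the symptoms become the AE and the ECG abnormality is explanatory. No seriousness or discontinuation condition is attached. The section also says that ECGs "will be obtained at screening, end of treatment, and when clinically indicated", and it refers to the screening and module schedules for timing.
- **Section 8.3.7 (Adverse events based on examinations and tests).** This covers worsening from baseline on assessments that the protocol mandates. The list names ECGs and ends with a catch-all for other safety assessments. Such worsening should "only be reported as AEs if they fulfil any of the SAE criteria or are the reason for discontinuation of treatment" with IP.

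Three other places bear on the point. Section 8.3.4 lists what an AE record holds, including CTCAE grade, investigator causality, action taken and outcome. Section 9.4.5 builds the AE summaries by grade and causality, and separately lists and summarises ECG data. Section 3 names AEs and SAEs as a safety endpoint.

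**The concern.** One section tells the site to report; the other, which names ECGs expressly, tells it not to unless one of two conditions holds. A site cannot obey both for a finding that meets neither condition, and nothing in the core text ranks the two sections. Two sites could therefore treat the same ECG differently. The finding would appear in the AE tables with a causality rating and a grade at one site, and only in the ECG listings and summaries at the other. The AE counts for each module would then partly reflect which page the site staff consulted.

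**Working it through.** No arithmetic applies. The check takes each kind of new ECG finding, applies both rules, and then looks for a clause that reconciles them.

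**Step 1. Apply both rules.**

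| New ECG finding | Section 8.2.5 | Section 8.3.7 | Agree? |
|---|---|---|---|
| Clinically significant and meets an SAE criterion | AE | AE | Yes |
| Clinically significant and the reason IP is stopped | AE | AE | Yes |
| Clinically significant with symptoms | Symptom is the AE | Symptom is collected anyway (Section 8.3.6) | In effect, yes |
| Not clinically significant, non-serious, IP not stopped for it | Not an AE | Not an AE | Yes |
| Clinically significant, asymptomatic, non-serious, IP not stopped for it | AE | Not an AE | **No** |

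The conflict is confined to the last row.

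**Step 2. Can that row occur at a scheduled ECG?** Yes. An end-of-treatment ECG is required by Section 8.2.5. Under Section 8.2.7 the visit takes place "as soon after the study drug is stopped as possible, preferably within 2 days of stopping drug"; where drug was already on hold, "the EOT visit should be performed within 7 days of the decision". On either route the visit follows the decision to stop, so a finding first seen there cannot normally be the reason for stopping. Of the two conditions in Section 8.3.7, only seriousness is left. The visit lies within the AE collection window, which runs "throughout the treatment period and including the 30-day follow-up period" (Section 8.3.2). A non-serious, clinically significant finding at that ECG is therefore an AE under Section 8.2.5 and not an AE under Section 8.3.7.

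**Step 3. On-treatment ECGs.** The core text schedules none between the first dose and end of treatment; it provides for ECGs when clinically indicated and leaves further times to the modules. Whether a clinically indicated ECG counts as protocol-mandated is not stated. A finding that leads to a hold and restart, such as the QTc entry in the footnote to Table 9, is a further case only if it does.

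**Step 4. Look for a reconciling clause.**

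- The symptom sentence in Section 8.3.7 covers laboratory values and vital signs, and the case at issue has no symptoms.
- The sentence on non-mandated parameters does not reach an ECG that is scheduled.
- The physical-examination sentence concerns examination findings.
- The important-medical-event criterion in Appendix B makes some ECG findings serious, but not every clinically significant one.
- Sections 8.2.1 and 8.2.2 send the reader to Section 8.3.7; Section 8.2.5 does not.
- The rule in Section 5 that a module overrides the core concerns eligibility and does not rank two core sections.

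No core clause resolves the conflict.

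**The case against.** The strongest reply is that little is at stake. Intervals and an overall evaluation are recorded for every ECG (Section 8.2.5), ECG data are listed and summarised (Section 9.4.5), and dose interruptions go into the eCRF (Section 6.4). Serious and treatment-stopping findings are AEs under both rules. This stands, and it limits the point to how a finding is classified. A reader might infer that ECG safety information would be lost; the documents do not support that.

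A second reply is that the restriction is deliberate: results that are summarised anyway need not be AEs as well. The stated reason, "The results from the protocol mandated laboratory tests and vital signs will be summarized in the clinical study report (CSR"), does not name ECGs, but Section 9.4.5 summarises them too, so the logic can be extended. It would therefore be too strong to say that the restriction has no rationale for ECGs. Even so, a deliberate restriction leaves Section 8.2.5 saying the opposite.

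A third reply is that a site would sensibly follow the ECG-specific section, and that unseen documents may settle the matter. Section 8.4.1 places full AE-reporting details in a Safety Handling Plan, Section 8.2.5 refers to an ECG manual, and the modules may add rules. Any of these might help in practice, but none removes the contradiction in the core text.

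Section 8.2.6 attaches T wave inversion or flattening to the words clinically significant. It is tempting to conclude that every such change is an AE under Section 8.2.5. That passage sets a trigger for an echocardiogram, and the Investigator reviews each ECG, so the conclusion does not follow.

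**Conclusion.** The contradiction is real, narrow and minor. It is an internal inconsistency that affects new, clinically significant, asymptomatic, non-serious ECG findings for which IP is not stopped. The clear instance is a finding first seen at end of treatment. Its consequence is confined to whether the finding gets an AE record, and so to AE counts in descriptive safety tables.

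Two stronger readings should be set aside:

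- **A numerical ceiling.** A reader might multiply about 30 patients by the two modules opened and take the product as the most end-of-treatment ECGs that could be affected. That is not a valid bound: the planned 30 are PSA-evaluable patients, non-evaluable patients may be replaced (Section 9.2), and module schedules may add ECG times. The frequency of such findings is unknown.
- **A missing grading step.** Section 9.4.5 states a CTCAE calculation for laboratory variables and none for ECGs. That detail is commonly left to the statistical analysis plan and is not a defect here.

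The conclusion assumes that the end-of-treatment ECG is protocol-mandated, as Section 8.2.5 indicates, and that no unseen module, Safety Handling Plan or ECG manual already sets the rule.

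**What to change.** Reconcile the two sections so that one AE-reporting rule applies to ECGs. One way is to add to the restrictive sentence in Section 8.3.7: *except clinically significant new ECG findings, which are reported as described in Section 8.2.5*. Narrowing Section 8.2.5 would also remove the conflict; what matters is that the two agree. Deleting the word ECGs from Section 8.3.7 is not enough, because the catch-all for other safety assessments would still cover them: ECGs sit under Section 8.2, Safety assessments.

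Add one sentence stating whether clinically indicated ECGs count as protocol-mandated.

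The cost is one clause and one sentence and, if the exception is adopted, a few more AE entries for sites. The change leaves laboratory and vital-sign reporting and all hold and discontinuation rules as they are.

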8.4.5 Management of AZD4635-related toxicities

AZD4635 management and discontinuation guidelines for non-hematologic toxicities (except hypertension) are shown in [Table 9](#). Inpatient dose re-escalation is not permitted. AZD4635 dose reduction guidelines are in Section 6 of the study-specific modules.

If a patient experiences a clinically significant and/or unacceptable toxicity not attributable to the disease or disease-related processes under investigation, dosing will be interrupted or the dose reduced and supportive therapy administered, as required. If the toxicity resolves or reverts to \leq CTCAE Grade 2 within 2 treatment weeks and the patient is showing clinical benefit per the Investigator, treatment with AZD4635 may be restarted. If the toxicity does not resolve to \leq CTCAE Grade 2 after 2 weeks of treatment then the patient should be withdrawn from the study and observed until resolution of the toxicity. Maximum drug holiday allowed is 2 weeks for non-immune-mediated toxicity.

Table 9 AZD4635 dose modifications and discontinuation criteria for non-hematologic toxicities (except hypertension)

NCI CTCAE Toxicity Grade	Action
Grade 1 or 2	None required
Grade 3 or 4 and/or clinically significant^a	Hold AZD4635
Toxicity resolved to Grade 1, Grade 2, or baseline <14 days	Restart AZD4635 at 1 dose level reduction
Toxicity remains Grade 3 to 4 or is clinically significant ^a >14 days	Discontinue AZD4635
Recurrence of Grade 3	Reduce 1 more dose level if module-specific guidance allows or if not discontinue AZD4635
Recurrence of Grade 3 cardiac event^a	Discontinue AZD4635
Recurrence of Grade 4	Discontinue AZD4635

^a Includes significant change in CK/CK-mb ratio (relative index >5%), increases in heart rate of +25 bpm (up to 100 to 125 bpm) for more than 24 hours or increase in heart rate >125 bpm for more than 12 hours), QTc prolongation >500 ms.

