
Grade 3 (systolic BP \geq160 mm Hg or diastolic BP \geq100 mm Hg); medical intervention indicated; more than one drug or more intensive therapy than previously used indicated
	
Initiate or maximize BP therapy as per local guidelines.
 
Consider consult with a BP management specialist
	
Increase frequency of monitoring until stabilized to BP $<$150/90 mmHg
	
May continue AZD4635 with optimization of antihypertensive management unless persistent BP-related clinical symptoms.
 
Hold AZD4635 if BP is not decreased to grade 2 within 48 hours after optimum therapy is instituted.
 
If BP is reduced to baseline or Grade 1 within 14 days and considered stable, AZD4635 may be resumed at original dose.
 
Discontinue AZD4635 if BP does not resolve to Grade 1 within 14 days.
 
Discontinue AZD4635 if BP systolic \geq180 mmHg and/or diastolic \geq110 mmHg)
 
Recurrence of Grade 3: Discontinue study drug.

Grade 4 Life-threatening consequences (e.g., malignant hypertension, transient or permanent neurologic deficit, hypertensive crisis); urgent intervention indicated
	
Initiate treatment per local guidelines, including hospitalization, ICU management, and IV therapy as necessary
		
Discontinue AZD4635

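### Under Protocol Section 8.3.7, non-serious asymptomatic laboratory or blood pressure events that change AZD4635 dosing or need drug treatment need not be reported as AEs

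*Protocol*

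**What the plan says.** Section 8.3.7 sets the AE rule for measurements that the protocol itself schedules: laboratory values, vital signs, ECGs and other safety assessments. Deterioration in these should "only be reported as AEs if they fulfil any of the SAE criteria or are the reason for discontinuation of treatment" with the IP. The stated reason is that the laboratory and vital-sign results get their own summary in the clinical study report.

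Two further routes follow in the same section:

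- With symptoms: "If deterioration in a laboratory value/vital sign is associated with clinical signs and symptoms, the sign or symptom will be reported as an AE"; in that case the measurement becomes supporting information.
- Without symptoms: a clinically relevant change is an AE only if the parameter is not one the protocol mandates.

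Laboratory tests and blood pressure (BP) are both mandated. Section 8.2.1 says of the Table 8 tests: "All protocol-required laboratory assessments, as defined in the table, must be conducted in accordance with the laboratory manual and the SoAs". Section 8.2.4 says that vital signs, including BP and pulse, "will be assessed according to the screening and module-specific SoA".

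The dose-modification tables describe events that fall short of discontinuation. Table 9 (non-hematologic toxicity except hypertension) holds AZD4635 for Grade 3 or 4 and, if the event resolves in under 14 days, says "Restart AZD4635 at 1 dose level reduction". Table 10 calls for starting or maximizing BP therapy at Grade 3 and says "Hold AZD4635 if BP is not decreased to grade 2 within 48 hours after optimum therapy is instituted". It allows resumption at the original dose once BP is stable at baseline or Grade 1 within 14 days.

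**The concern.** AEs and SAEs head the safety endpoints in Table 3, and Section 9 puts safety and tolerability in the study's primary aim. The Section 9.4.5 tables of Grade 3-or-higher and causally related AEs are built from reported AEs. An event serious enough to interrupt or reduce the study drug, or to need new drug treatment, is what a reader expects to find there. If Section 8.3.7 keeps it out, the AE tables understate tolerability problems in a study meant to choose combinations to take forward. The loss also cannot be repaired at analysis: the causality judgement (Section 8.3.5) and the action taken with the IP (Section 8.3.4) are collected per AE, so without an AE entry neither is recorded.

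**Working it through.** There is no planned figure to reproduce. The check traces event types through the rule.

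**Step 1. Triggers.** For a mandated laboratory value or vital sign, Section 8.3.7 gives three ways in: an SAE criterion, discontinuation of IP, or an accompanying sign or symptom. Interruption, dose reduction and need for treatment are not among them.

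**Step 2. Events the protocol foresees.** Rows 1 to 3 assume no symptoms and a non-serious judgement.

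| Event | Outcome in the protocol | AE under 8.3.7? | Still visible in |
|---|---|---|---|
| 1. First Grade 3-4 non-hematologic laboratory toxicity, resolved in under 14 days | Hold, restart one level lower (Table 9) | Not required | Laboratory CTCAE grades; hold and reduction counts |
| 2. First Grade 3 BP, systolic below 180 and diastolic below 110, controlled within 48 hours | BP therapy, dosing may continue (Table 10) | Not required | BP summary; concomitant medication |
| 3. As row 2, but not at Grade 2 within 48 hours; Grade 1 within 14 days | BP therapy, hold, resume at original dose (Table 10) | Not required | BP summary; concomitant medication; hold count |
| 4. BP Grade 4, systolic 180 or more, diastolic 110 or more, unresolved at 14 days, or recurrent Grade 3 | Discontinue AZD4635 (Table 10) | Yes | AE tables |
| 5. Potential Hy's Law case newly arising on treatment | Reported as SAE (Appendix E 4.2) | Yes | AE tables |

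For BP, the Grade 3 gap is therefore a first episode with systolic 160-179 or diastolic 100-109, neither reaching 180 or 110, that resolves within 14 days. Treated BP below Grade 3 is also outside the rule.

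**Step 3. What the other summaries recover.** Section 9.4.5 calculates CTCAE grade for laboratory variables; it states no grading for BP, which is listed and summarized. Section 9.4.3 counts patients with at least one interruption or reduction, but provides for reasons only at discontinuation. Row 1 thus keeps its grade and its dose change but loses the link between them. Rows 2 and 3 lose the grade as well.

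**Step 4. ECGs.** Section 8.2.5 makes a clinically significant ECG abnormality absent at baseline an AE. Section 8.3.7 places ECGs under the restriction. The two rules differ.

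**Step 5. Scale.** The synopsis plans about 30 patients per module. With k patients left out, incidence falls by k/30:

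- k = 1: 1/30 = 3.3 points
- k = 2: 2/30 = 6.7 points
- k = 3: 3/30 = 10.0 points

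These values of k are assumptions that show the range; the documents give no rate. If k = 3 were every case, the AE table would read 0/30 (exact 95% upper limit 1 - 0.025^(1/30) = 11.6%) instead of 3/30 = 10% (2.1% to 26.5%).

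**The case against.** The rule is deliberate and its reason is coherent. Mandated measurements have their own summary and are safety endpoints alongside AEs, so Section 8.3.7 avoids counting them twice. Laboratory grades are calculated, holds and reductions are recorded in the eCRF (Section 6.4) and counted, and raw BP is summarized. An investigator may also class an event as medically important under Appendix B 2, which makes it an SAE. Module Appendices K and L, which hold the AEs of special interest, are not shown and may require more. All of this stands, and it narrows the point.

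It does not close it. A summary of measurements carries no causality or action taken, and a brief, treated Grade 3 BP rise can disappear in averaged values. Section 8.3.6 and the AE definition in Appendix B 1, which includes abnormal laboratory findings, might lead some sites to report anyway. But Section 8.3.7 is the specific rule and is worded restrictively, so rates would then depend on site habit.

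A reader might infer more than the text supports:

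- That such events can never reach the AE tables. Rows 4 and 5, SAE judgement and symptomatic cases all do.
- That the rule is upside down in severity because non-mandated parameters are treated more strictly. Mandated versus non-mandated is not a severity scale; non-mandated parameters simply have no other summary.
- That BP events lead to unreported dose reductions. Table 10 contains no reduction.
- That all laboratory toxicity driving dose changes is affected. Table 9 covers non-hematologic toxicity only.
- That the related Grade 3 hypertension in Section 2.3 shows the gap. It was an SAE, which this rule would capture.

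**Conclusion.** The gap is real but bounded. Followed as written, Section 8.3.7 does not require an AE for a non-serious, asymptomatic laboratory or BP event that holds AZD4635, reduces it under Table 9, or needs new or intensified drug treatment under Table 10. The main losses are treated first-episode Grade 3 BP, for which no grading is stated, and the attribution of a hold or reduction to its cause. The cost is about 3.3 percentage points of AE incidence per omitted patient in a module of 30. How many patients that would be cannot be taken from the documents.

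This rests on the core protocol alone and on sites applying the rule literally. No primary efficacy endpoint, sample size or efficacy analysis set is affected, and safety is descriptive throughout. It should be fixed because it biases a stated safety endpoint in the favourable direction and is cheap to correct. It is not a defect that invalidates the study.

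**What to change.** Extend the reporting sentence in Section 8.3.7. Besides SAE criteria and discontinuation, a deterioration in a mandated measurement becomes an AE if it leads to interruption or dose reduction of any IP, or if it is CTCAE Grade 3 or higher and requires medical treatment. Limiting the treatment trigger to Grade 3 or higher avoids bringing in every treated lower-grade BP change. Reconcile the ECG wording with Section 8.2.5 in the same edit, and check Appendices K and L for reporting rules that already cover part of this.

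Tables 9 and 10 need no change; this concerns what is reported, not how patients are managed.

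The cost is one sentence in the protocol, a matching line in the eCRF guidance, a few more AE entries, and a slightly less favourable AE table. The change belongs in the protocol, because a later analysis cannot supply causality and action-taken data that were never collected.
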